### 2.3 Exploratory Molecular Endpoints

1. To determine the proportion of patients who achieve mutation clearance to <0.1%, after 3 cycles of decitabine.
2. To determine whether PB or BM has the greater sensitivity for detecting residual mutation burden using a sensitive sequencing technology such as Haloplex.
3. To determine *TP53* clonal burden reduction after consolidation with stem cell transplantation using a sensitive sequencing technology such as Haloplex.
4. To determine whether decitabine induces consistent methylation signatures using whole genome bisulfite sequencing.
5. To determine whether decitabine induces consistent expression signatures using RNA sequencing, and whether these correlate with methylation signatures.

## 3.0 PATIENT SELECTION

### 3.1 Inclusion Criteria

1. *TP53* mutant AML. The presence of a *TP53* mutation should be determined by Genoptix (or institutional preferred equivalent assay). Detection of a *TP53* mutation at the time of initial diagnosis is sufficient for enrollment at the time of relapsed/refractory disease. Detection of a *TP53* mutation in either the peripheral blood or bone marrow is adequate for enrollment. (Refer to Appendix B for definition of *TP53* mutant AML.) Alternatively, patients who have not had *TP53* mutation analysis performed, but who have > 20% *TP53* positive cells by immunohistochemistry detected on a bone marrow aspirate may also be enrolled, provided that mutation analysis is requested at the time of enrollment.
2. Relapsed/refractory AML following 7+3 (or similar cytarabine containing induction chemotherapy for AML) disease detected by one of the following methods:
  - Bone marrow blasts > 5%, or
  - Hematologics flow cytometry assay (threshold > 0.5%) (alternative equivalent assay may be substituted), or
  - Persistent cytogenetic abnormality (e.g. del5, del17p, etc) by FISH or conventional karyotyping, or
  - Persistent *TP53* mutation (at least 5 variant reads with at least 50x coverage) determined by Genoptix (or institutional preferred equivalent assay).

Patients with > 10% blasts on a Day +14 bone marrow biopsy following 7+3 may either be enrolled or may be treated with a course of standard re-induction (e.g. 5+2 or similar) and then re-evaluated for response. Eligible patients will meet any of the above criteria on a subsequent biopsy.

3. Bone marrow and organ function as defined below:
  - Peripheral white blood cell count < 50,000/mcl (patients may receive hydroxyurea as necessary for cytoreduction),
  - Total bilirubin < 1.5 x upper limit of normal,
  - AST and ALT < 2.5 x upper limit of normal,
  - Serum creatinine < 2.0 x upper limit of normal, and,
4. At least 18 years of age.
5. Women of childbearing potential and men must agree to use adequate contraception (hormonal or barrier method of birth control, abstinence) prior to study entry and for the duration of study participation. Should a woman become pregnant or suspect she is pregnant while participating in this study, she must inform her treating physician immediately
6. Ability to understand and willingness to sign an IRB approved written informed consent document (or that of legally authorized representative, if applicable)
7. Performance status  $\leq 3$

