## 2.0 OBJECTIVES

### 2.1 Primary Endpoint

To determine the 1-year OS in patients with *TP53* mutations treated with at least one dose of decitabine compared to historic controls (OS = 25%).

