### **15.2 Analysis Populations**

Intent-to-Treat - Defined as all patients who receive at least one dose of decitabine.

Efficacy-Evaluable - Defined as all patients who receive at least one cycle of treatment.

Safety - Defined as all patients with at least one dose of decitabine.

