## **B. Primary Endpoint Analysis**

The primary end-point of this phase II study is the 1-year survival in primary relapsed/refractory AML patients treated with decitabine.

Overall survival (OS) is defined as the time from enrollment to death due to any cause. For a patient who is not known to be alive at the end of study follow up, observation of OS is censored on the date the patient was last known to be alive (i.e. date of last contact).

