## **C. Overall survival analysis**

Kaplan-Meier curves depicting OS in the study population compared to historical control will be generated. Additionally, the median OS and the probability of OS from 1 month to the end of the follow-up period will be reported at pre-specified intervals. The associated 2-sided 90% CIs will be calculated using the complementary log-log transformation method (Collett 1994).

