## **D. Interim Analysis**

The estimated duration of the study is approximately 3 years from enrollment of the first patient to the final analysis. An interim analysis for OS will be performed at 1.5-year (where approximately one-fourth of patients will have at least 1-year follow-up if assuming uniform accrual) and the conditional power will be calculated for futility analysis based on the accumulated data. Conditional power is defined as the projected power to reject the null hypothesis (that treatment of *TP53*-mutated AML patients with relapsed/refractory disease is associated with 1-year survival of 25%) at the end of the study given the data accrued up to the interim analysis. Therefore, a small value of conditional power indicates a highly likely, if not inevitable, conclusion of negative finding given the current data. If conditional power of 0.3 or less is obtained at the interim analysis, an early termination due to futility will be recommended.

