### **G. Statistical Power Justification**

**Primary endpoint.** The primary endpoint of this study is the 1-year overall survival (OS) which will be compared to historical data (1-year OS=25%). Assuming survival times following an exponential distribution and an additional 1-year follow-up period after the accrual period, a total of 60 patients will be enrolled and this allows us 85% power at 1-sided  $\alpha=0.05$  to detect 15% difference (40% vs. 25%) in 1-year OS.

**Secondary endpoints.** A power analysis was performed using two-sample t-test for between-group difference and paired t-test for the change over time. For tumor clearance, this will provide > 99% power to detect a 10% difference in the means at two separate time points for clones with 6 or more variants, and > 98% power to detect a 15% difference if there are 3 or more variants per clone with  $\alpha = 0.05$  (power will decrease to 91% and 82%, respectively, in cases where the standard deviation is 4.7%, the maximum we have observed thus far). For pharmacologic correlations, we anticipate 85% power to determine a 25 ng/ml difference between the average Cmax of 45 evaluable responders and 55 evaluable non-responders with an anticipated average Cmax of 70 ng/ml and a standard deviation of 40 ng/ml within the entire cohort, and with  $\alpha = 0.05$ . We believe a less significant difference would not be sufficient to warrant application in clinical decision making (i.e. whether to continue therapy for more than 1 cycle). We anticipate 99% power to determine a difference of 20% in the reduction of bone marrow methylcytosine between 45 evaluable responders and 55 evaluable non-responders with an expected standard deviation of 15% and  $\alpha = 0.05$ . The difference in methylcytosine reduction previously observed was 30% between patients achieving CR/PR and those with only hematologic improvement.

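### The primary 1-year OS analysis has no TP53 condition, so patients enrolled on p53 immunohistochemistry who prove wild-type can be tested against a 25% benchmark set for TP53-mutated disease

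*Combined protocol and SAP*

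**What the plan says.** **Entry.** The usual route in Section 3.1 is a detected TP53 mutation, with Appendix B as the definition: variant allele frequency of at least 10%, at least 50 total reads, at least 5 variant reads, and a germline check. The alternative route takes patients who have not been tested, if more than 20% of marrow cells are TP53-positive on IHC, "provided that mutation analysis is requested at the time of enrollment". A request is enough. The result need not be positive, or even available, before dosing.

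**Target and null.** Section 2.1 limits the primary objective to patients with TP53 mutations who received at least one dose, against a historical 25%. Section 15.4.D states the null for the same group: "mutated AML patients with relapsed/refractory disease is associated with 1-year survival of 25" percent. Section 15.4.G powers for a "15% difference (40% vs. 25%) in 1-year OS" with 60 patients, one-sided alpha 0.05 and 85% power.

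**Analysis.** Section 15.2 reads "Intent-to-Treat - Defined as all patients who receive at least one dose of decitabine". The efficacy-evaluable and safety sets likewise depend only on treatment received. Section 15.4.B gives the primary endpoint as "1-year survival in primary relapsed/refractory AML patients treated with decitabine", and 15.4.C plans curves "depicting OS in the study population compared to historical control". Neither names an analysis set or mentions TP53. The ITT set is named only in 15.4.E, for secondary endpoints.

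**The concern.** The objective and the null are about TP53-mutated disease, while the sets and the primary analysis text are about everyone dosed. An analyst who programs from 15.2, 15.4.B and 15.4.C keeps a wild-type patient. One who works from 2.1 and 15.4.D drops that patient. In an open-label single-arm trial whose only comparator is a fixed rate, this choice could be made after survival is known.

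The choice can move the result either way. Section 1.2 reports worse survival with TP53 mutations (3-year OS 3% versus 28%). If that direction carries over, wild-type patients raise 1-year OS with no drug effect in the target group. Section 1.2 also links response to decitabine to TP53 mutation. If wild-type patients gain little, keeping them dilutes a real effect. Secondary endpoint 1 has the same gap, since it compares response in TP53-mutated patients with 10-15%.

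**Working it through.** **Inputs from the documents.** N = 60, null 25%, alternative 40%, one-sided alpha 0.05, stated power 85% (15.4.G).

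**Inputs assumed.** The number of wild-type patients among the 60, and their 1-year OS. The documents give no share enrolled by IHC, no IHC false-positive rate and no 1-year OS for wild-type relapsed/refractory patients. I use 3 or 6 patients (5% or 10%) and 1-year OS of 40% or 50%.

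**1. The plan's own figure.** Use a one-sample normal test of a proportion with the null variance.

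- Standard error: sqrt(0.25 × 0.75 / 60) = 0.0559.
- Power: Φ(0.15/0.0559 − 1.645) = Φ(2.683 − 1.645) = 85.0%.

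This reproduces the stated 85%.

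**2. False-positive rate with wild-type patients included.** Treat 1-year survival as binary. Let k patients be wild-type with survival w and the others sit at the null, so the number alive is Bin(60 − k, 0.25) + Bin(k, w). The plan gives no cutoff in patients, so two are shown: 21 of 60 (exact size 5.4%, slightly above alpha) and 22 of 60 (exact size 3.0%, within alpha).

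| Wild-type patients | Wild-type 1-year OS | Mixed 1-year OS | P(≥21 alive) | P(≥22 alive) |
|---|---|---|---|---|
| 0 | – | 25.0% | 5.4% | 3.0% |
| 3 | 40% | 25.75% | 7.1% | 4.0% |
| 3 | 50% | 26.25% | 8.3% | 4.8% |
| 6 | 40% | 26.5% | 9.1% | 5.3% |
| 6 | 50% | 27.5% | 12.2% | 7.4% |
| 3 or 6 | 25% | 25.0% | 5.4% | 3.0% |

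The mixed OS is [(60 − k) × 25% + k × w] / 60. For k = 6 and w = 40% it is (54 × 25% + 6 × 40%) / 60 = 26.5%.

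**3. The opposite direction.** Put mutants at 40% and leave 6 wild-type patients at 25%. Power falls from 82% to 75% at 21 of 60, and from 74% to 66% at 22 of 60.

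**4. Cost of leaving wild-type patients out.** By the formula in step 1, 57 patients give 83.4%. With 54 patients the standard error is sqrt(0.25 × 0.75 / 54) = 0.0589, and power is Φ(2.546 − 1.645) = 81.6%.

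**The case against.** The strongest reply is that the plan already answers the question. Section 2.1 says TP53 mutations, and the null in 15.4.D, inside the statistical section, says so again. On that reading wild-type patients are simply outside the primary test. This stands in part. A reader might infer from 15.2 that the plan commits to testing every dosed patient against 25%, and the documents do not support that: no section assigns the primary test to the ITT set. They do not assign it to a TP53-confirmed set either, and no such set is defined. What remains is an unresolved conflict.

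A second reply concerns size. A reader might infer that the false-positive rate doubles or triples. Against 5.4%, only one of the four inflating scenarios above (6 patients at 50%) more than doubles it. Tripling needs something like 6 wild-type patients at 65% OS, which gives 17.9%. That 65% is what the 28% 3-year figure becomes under exponential survival (0.28^(1/3) = 0.654). The 28% describes conventional chemotherapy, not patients who are refractory or relapsed after induction, and 65% is well above the trial's own 40% target. These patients are also selected for p53 positivity, so general wild-type survival need not apply to them. This reply stands: the documents support neither input.

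A third reply is that restricting to confirmed patients can itself bias the result. That also stands, but for missing and indeterminate results only. Testing need only be requested, so failed or absent results need not be random. Section 3.1 also admits low-burden disease (for example, flow cytometry above 0.5%), and a truly mutated patient whose only sequenced sample is low-burden could miss the 10% allele-frequency threshold in Appendix B.

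**Conclusion.** The concern holds as a conflict between Sections 2.1 and 15.4.D on one side and 15.2, 15.4.B and 15.4.C on the other, together with an IHC route that has no rule for a wild-type or missing result. Followed as written, the analysis text allows wild-type patients into a test against a TP53-mutant benchmark.

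The size is conditional. With 5-10% of patients wild-type at 40-50% 1-year OS, the false-positive rate rises from 5.4% to about 7-12% at 21 of 60, or from 3.0% to about 4-7% at 22 of 60. There is no inflation if wild-type OS is 25%, and power is lost if mutants benefit and wild-type patients do not. These figures treat 1-year survival as a binary outcome. A general claim of a doubled or tripled error rate is not supported. The change should be made because it is cheap and closes off a choice that could otherwise be made with outcomes in view.

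**What to change.** In 15.2 and 15.4.B:

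- Name the primary set as dosed patients with a TP53 mutation meeting Appendix B on a diagnostic or pre-treatment sample, whenever the result returns. Refer to this set in 15.4.C, 15.4.D and the analysis of secondary endpoint 1.
- Exclude only patients with an adequate pre-treatment result that is wild-type. Report their outcomes separately and keep them in the safety set.
- State in advance, without reference to outcome, how missing, failed or low-burden indeterminate results are classified. One option is to keep them in the primary set and add a sensitivity analysis without them.
- Report all dosed patients as a sensitivity analysis.
- Say whether wild-type patients are replaced.

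The cost is wording plus a small loss of power. If 6 of 60 are excluded and not replaced, power goes from 85% to about 82% by the formula that reproduces the plan's figure. Keeping 60 confirmed patients would need 60 / 0.90, or 67 enrolled, if 10% prove wild-type. TP53 status is fixed before treatment, so excluding patients with an adequate wild-type result does not select on outcome. That assurance does not extend to missing results, which is why they need their own rule.

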### **3.2 Exclusion Criteria**

1. Prior treatment with either decitabine or azacitidine, or an investigational agent.
2. Acute promyelocytic leukemia with *PML-RARA* or t(15;17).
3. History of HIV, Hepatitis B, or Hepatitis C infection.
4. Concurrent illness including, but not limited to, ongoing uncontrolled infection, symptomatic NYHA class 3 or 4 congestive heart failure, unstable angina pectoris, or cardiac arrhythmia.
5. Radiation therapy within 14 days of enrollment.
6. Chemotherapy administration in the 7 days preceding enrollment with the exception of hydroxyurea, which can be continued until through Cycle 2. A washout period for oral tyrosine kinase inhibitors (e.g. Jakafi, etc) is not required, although tyrosine kinase inhibitors therapy must be discontinued prior to enrollment.

7. Malignancies (other than AML) requiring active therapy or diagnosed within the last year, with the exception of non-melanoma skin cancer which can be treated or in situ malignancies (such as cervical, breast, prostate, etc.).
8. Currently receiving any other investigational agents.
9. Known CNS leukemia or testicular involvement of leukemia.
10. A history of allergic reactions attributed to compounds of similar chemical or biologic composition to decitabine or other agents used in the study.
11. Pregnant and/or breastfeeding. Women of childbearing potential must have a negative urine pregnancy test within 7 days of study entry.

### **3.3 Inclusion of Women and Minorities**

Both men and women and members of all races and ethnic groups are eligible for this trial.

## **4.0 REGISTRATION PROCEDURES**

**Patients must not start any treatment on protocol prior to registration through the Siteman Cancer Center. Pre-study assessments, such as blood testing, bone marrow biopsy or others as listed under baseline evaluation (Section 5.1.2) are allowed.**

The following steps must be taken before registering patients to this study:

1. Confirmation of patient eligibility by Washington University
2. Registration of patient in the Siteman Cancer Center database
3. Assignment of unique patient number (UPN)

Once the patient has been entered in the Siteman Cancer Center OnCore database, the WUSM coordinator will forward verification of enrollment and the UPN via email.

### **4.1 Confirmation of Patient Eligibility**

Confirm patient eligibility by collecting the information listed below and scanning and emailing it to the research coordinator listed in the *Siteman Cancer Center Clinical Trials Core Protocol Procedures for Secondary Sites* packet at least one business day prior to registering patient:

1. Your name and contact information (telephone number, fax number, and email address)
2. Your site PI's name, the registering MD's name, and your institution name
3. Patient's race, sex, and DOB
4. Three letters (or two letters and a dash) for the patient's initials
5. Currently approved protocol version date

6. Copy of signed consent form (patient name may be blacked out)
7. Planned date of enrollment
8. Completed eligibility checklist, signed and dated by a member of the study team
9. Copy of appropriate source documentation confirming patient eligibility

#### **4.2 Patient Registration in the Siteman Cancer Center OnCore Database**

Registrations may be submitted Monday through Friday between 8am and 5pm CT. Urgent late afternoon or early morning enrollments should be planned in advance and coordinated with the Washington University research coordinator. The research coordinator or his/her delegate will confirm registration by email within one business day. Verification of eligibility and registration should be kept in the patient chart.

All patients at all sites must be registered through the Siteman Cancer Center OnCore database at Washington University.

#### **4.3 Assignment of UPN**

Each patient will be identified with a unique patient number (UPN) for this study. Patients will also be identified by first, middle, and last initials. If the patient has no middle initial, a dash will be used on the case report forms (CRFs). All data will be recorded with this identification number on the appropriate CRFs.

### **5.0 INVESTIGATION PLAN**

#### **5.1 Summary**

See Section 10 for synoptic table.

Patients will receive decitabine 20 mg/m^2/day as a 1-hour infusion on consecutive days 1-10 of each 28-day cycle. Decitabine dose will be calculated on baseline weight (obtained within a week of the start of cycle 1). Decitabine dose should be recalculated for weight changes above or below 10% from baseline weight

Patients with clinical evidence of progressive disease or relapse (see Section 12 for definitions) should undergo a bone marrow biopsy to evaluate for progression.

After 2 cycles, patients with progressive disease or relapse (a clear progression with at least >20% bone marrow blasts and an increase of at least 50% from prior biopsy) should be removed from protocol and proceed to salvage treatment according to center preference.

Transplant eligible patients with PR after 3 cycles, may be removed from protocol and proceed to salvage treatment or transplant according to center preference.

Transplant eligible patients with a suitable donor who achieve mLFS, CR, CRc, or CRi, may proceed to transplant after at 3 cycles (Section 5.5).

Transplant ineligible patients with CR, CRc or CRi, PR will continue on maintenance doses (see below and Section 6.3) until progression or death, whichever occur first.

Transplant ineligible patient with SD after cycle 4 may be removed from protocol and proceed to alternative treatment or continue on protocol according to treating physician's preference.

After Cycle 1, patients with blast counts < 5% may reduce decitabine dose from 20 mg/m^2/day x 10 days to 20 mg/m^2/day x 5 days.

For all other patients, after Cycle 2, decitabine administration dose will be decreased to 20 mg/m^2/day for 5 consecutive days (Days 1-5) every 28 days (unless otherwise specified) to limit myelosuppressive toxicity.

Peripheral blood sampling and bone marrow biopsies with aspirate will be performed pre-study, on Cycle 1 Day 10 ± 2, Cycle 1 Day 28 ± 4, on Cycle 2 Day 28 ± 4, on Cycle 3 Day 28 ± 4, and at progression or relapse. Patients will provide a skin biopsy sample pre-study; a buccal swab can be performed for patients who decline skin biopsy. A buccal swab will be collected on Cycle 2 Day 28 ± 4.

Following Cycle 3, bone marrow biopsies should be performed at the discretion of the treating physician to assess for response and for relapse or progression.

If at any bone marrow collection the aspirate is a “dry tap”, two additional tubes of blood (10 mL each) will be collected and banked.

#### **A. Pre-study Procedures**

Pre-study procedures must take place no more than 28 days prior to the first dose of decitabine except where noted below.

- Bone marrow aspirate and biopsy. Standard bone marrow procurement procedures will be followed for collection of the tissue. Assessments performed on bone marrow will include correlative studies, morphologic assessment, flow cytometry, cytogenetics, and FISH.
- Bone marrow or peripheral blood for flow cytometry.
- Collection and banking of bone marrow aspirate and peripheral blood.
- Skin biopsy sample: Patients who decline to undergo a skin biopsy can provide a buccal swab as alternative. There is no required time frame for this sample; it may have been collected months or even years prior to the first dose of decitabine. If WBC at enrollment is > 30,000/μl, the skin biopsy should be collected at C1D28.

## **B. Baseline Evaluation**

Baseline evaluations must take place no more than 7 days prior to the first dose of decitabine.

- Medical history
- Physical exam including height, and weight.
- CBC with differential and platelets
- Serum chemistries, including, albumin, creatinine, total bilirubin, AST, ALT, LDH
- Urine  $\beta$ HCG pregnancy test in women of childbearing age

